7.6.3 Vineland Adaptive Behavior Scales II (VABS-II)

The Vineland Adaptive Behavior Scales test measures adaptive behaviors, including the ability to cope with environmental changes, to learn new everyday skills, and to demonstrate independence. It is an instrument that supports the diagnosis of intellectual and developmental disabilities in subjects aged birth to 90 years. This test measures 5 key domains: communication, daily living skills, socialization, motor skills, and the adaptive behavior composite (a composite of the other four domains). The raw scores will be converted to domain standard scores (mean 100, SD 15) and domain-specific age equivalents, by referring to the appropriate conversion tables in the VABS-II manual (Sparrow, 2005). Tabular summaries of the age equivalent and DQ for each subdomain (expressive, written, personal, domestic, community, interpersonal relationships, play and leisure time, coping skills, gross, and fine) and the standard scores for domains, and the corresponding change from baseline will be presented at each assessment time point from baseline. VABS-II data will be presented in a by-subject listing.

A spaghetti plot of mean age equivalent score against chronological age will be presented. On the graph the time when 10 mg subject switched to 45 mg will be indicated.

7.6.4 Four Point Scoring System (FPSS)

The FPSS is a Sanfillipo Syndrome -specific disability assessment, developed by Meyer et al (Meyer, 2007) which assesses motor function, expressive language, and cognitive function on a 0 to 3 point scale and can be used for individuals of all ages. A score of 3 points is assigned for normal function, 2 points for beginning of regression, 1 point for severe level of regression, and 0 points for lost skills. The total disability score (TDS) is the average of the motor function, speech, and cognitive function scores.

Tabular summaries of the FPSS domain scores and the TDS will be presented at each assessment time point. The corresponding change from baseline will be summarized as well. FPSS data will be presented in a by-subject listing.

7.7 Analysis of Biochemical Endpoints

7.7.1 Total Heparan Sulfate Levels

The observed values at each visit and the change from baseline to each of the post-baseline visits will be descriptively summarized for CSF total heparin sulfate levels by dose group. Heparin sulfate levels (CSF) will be presented in a by-subject listing.

Graphical plot of mean CSF total HS levels across time will be presented. In addition, a spaghetti plot of total heparin sulfate levels over time will be presented. The impact of positive serum anti-rhHNS antibody result will also be explored graphically using a spaghetti plot and/or individual subject plots. Urine GAG levels will be presented in a by-subject listing.

7.8 Analysis of Imaging Endpoints

7.8.1 Brain MRI

Although several MRI parameters will be captured, the analysis will focus primarily on the grey matter volume, the white matter volume and the intracranial CSF volume (ventricles plus additional CSF space). The observed values at each visit and changes from baseline to each of the post-baseline visits will be descriptively summarized for these MRI parameters by dose group. Brain MRI data will be presented in a by-subject listing.

A spaghetti plots of MRI parameters against chronological age will be presented.

7.9 Safety Analysis

The safety parameters include: AEs, ECG, standard hematology, serum chemistry, urinalysis, CSF standard chemistry, and anti-rhHNS antibody.

7.9.1 Adverse Events

Aes will be recorded throughout the study and at early termination. Aes will be coded using the Medical Dictionary for Regulatory Activities (MedDRA) version 13.1 or higher.

Treatment-emergent Aes, defined as all Aes from the time of the surgery for first IDDD implantation in HGT-SAN-055 to the last day of reporting period (or cut-off date), will be summarized by treatment group. The summary will include the number and percentage of subjects with any AE, any drug-related AE, any surgery-related AE, any IDDD-related AE, any IT administration process-related AE, any severe AE, any serious AE (SAE), any serious drug related AE, and any AE that lead to discontinuation.

Treatment emergent Aes will be summarized by system organ class (SOC) and preferred term by dose group. The number and percentage of subjects experiencing an AE will be tabulated; recurrent Aes observed within a subject will be counted once. Furthermore, treatment-emergent Aes deemed as possibly/probably or definitely related to device surgical procedure, IDDD, investigational product, and IT administration process will be summarized separately. Treatment-emergent SAEs and treatment-emergent Aes which lead to study discontinuation will be similarly summarized.

By-subject listings will be provided for treatment-emergent Aes, treatment-emergent SAEs, deaths, and treatment-emergent Aes leading to discontinuation.

In general, an AE will be considered a treatment emergent AE if it cannot be definitively categorized by the available components (day, month, year) of the AE onset date with respect to the date of the IDDD implantation.

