5.2 Primary Endpoints

The primary endpoints of this study were related to the long-term safety of intrathecal HGT-1410 administration. The safety endpoints were:

[figure not shown]
- AEs (type and severity)
- changes in clinical laboratory testing (serum chemistry including liver function tests, hematology, and urinalysis)
- electrocardiograms (ECG)
- CSF chemistries (including cell counts and inflammatory markers)
- anti-rhHNS antibodies (in CSF and serum).

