6.3 Handling of Missing Data

If data at the baseline visit are not available, then the most recent available pre-treatment visit will be considered as baseline. Missing or partial AE dates will not be imputed. However, a conservative approach will be adopted in such cases so that the AE will be deemed to be treatment emergent if it cannot be definitively categorized to have occurred prior to surgery for IDDD implantation.

7 Data Displays

Tabular summaries will be presented by rhHNS dose group (10 mg, 45 mg, 90 mg). Data listings will be presented for every dataset described under this section. Data listings will be sorted by rhHNS dose group, rhHNS dose, site number, and subject number.

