10.2 Appendix II – List of Statistical Tables

Table	Table Title
10.1	Demographic and Baseline Characteristics
10.1.1:	Subject Disposition by Study and rhHNS Dose Group – Safety Population
10.1.2:	Demographics and Baseline Characteristic by rhHNS Dose Group – Safety Population
10.1.3:	Treatment Exposure by rhHNS Dose Group – Safety Population
10.2	Efficacy
10.2.1.1:	Observed Value and Change from Baseline in BSID-III Age-equivalent Scores (Months) by rhHNS Dose Group – Safety Population
10.2.1.2:	Observed Value and Change from Baseline in BSID-III DQ Scores (%) by rhHNS Dose Group – Safety Population
10.2.2.1:	Observed Value and Change from Baseline in BSID-III/KABC-II Age-equivalent Scores (Months) by rhHNS Dose Group – Safety Population
10.2.2.2:	Observed Value and Change from Baseline in BSID-III/KABC-II DQ Scores (%) by rhHNS Dose Group – Safety Population
10.2.3.1:	Observed Value and Change from Baseline in VABS-II Domains Standard Scores by rhHNS Dose Group – Safety Population
10.2.3.2:	Observed Value and Change from Baseline in VABS-II Sub-Domains Age-equivalent Scores (Months) by rhHNS Dose Group – Safety Population
10.2.3.3:	Observed Value and Change from Baseline in VABS-II Sub-Domains DQ Scores(%) by rhHNS Dose Group – Safety Population
10.2.4:	Observed Value and Change from Baseline in FPSS Domain Scores/Total Disability Scores by rhHNS Dose Group – Safety Population
10.2.5:	Observed Value and Change from Baseline in CSF Heparan Sulfate Levels by rhHNS Dose Group – Safety Population
10.2.6:	Observed Value and Change from Baseline in Brain MRI Parameters by rhHNS Dose Group – Safety Population
10.3	Safety
10.3.1.1:	Summary of Subjects with Treatment Emergent Adverse Events by rhHNS Dose Group – Safety Population
10.3.1.2:	Treatment Emergent Adverse Events by System Organ Class, Preferred Term, and rhHNS Dose Group – Safety Population
10.3.1.3:	Treatment Emergent Adverse Events by System Organ Class, Preferred Term, Severity, and rhHNS Dose Group – Safety Population
10.3.1.4:	Summary of Device Surgical Procedure Related Treatment Emergent Adverse Events by System Organ Class, Preferred Term, and rhHNS Dose Group - -Safety Population
10.3.1.5:	Summary of Device Related Treatment Emergent Adverse Events by System Organ Class, Preferred Term, and rhHNS Dose Group – Safety Population
10.3.1.6:	Summary of IT Administration Process Related Treatment Emergent Adverse Events by System Organ Class, Preferred Term, and rhHNS Dose Group- Safety Population

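### The treatment-emergent definition in SAP 7.9.1 has no clause for an AE that began before the first IDDD surgery and later worsened (minor)

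*SAP*

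**What the plan says.** SAP 7.9.1 (Adverse Events) gives the start of the window as "Treatment-emergent Aes, defined as all Aes from the time of the surgery for first IDDD implantation in HGT-SAN-055" and its end as "to the last day of reporting period (or cut-off date), will be summarized by treatment group". The last paragraph of that section deals with events that cannot be placed with certainty. The variable it names for placing them is the "available components (day, month, year) of the AE onset date with respect to the date of the IDDD implantation".

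SAP 6.3 does not impute missing or partial AE dates. Instead, "the AE will be deemed to be treatment emergent if it cannot be definitively categorized to have occurred prior to surgery for IDDD implantation".

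SAP 5.2 lists AEs first among the primary endpoints and names both their type and their severity. Appendix II opens the AE tables with 10.3.1.1, "Summary of Subjects with Treatment Emergent Adverse Events by rhHNS Dose Group". The other eight AE tables (10.3.1.2 to 10.3.1.9) and the four AE listings in Appendix IV (12.2.7.1 to 12.2.7.4) carry the same treatment-emergent restriction in their titles.

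**The concern.** A treatment-emergent definition usually has two limbs: events that start in the treatment window, and events already present that get worse in it. This SAP has only the first. An AE with a fully known onset before the first IDDD surgery is not treatment-emergent, whatever happens to it afterwards, if it stays a single record under its original onset date.

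Long-term safety and tolerability is the primary objective (SAP 3.1), and severity is part of the primary AE endpoint. A rule that looks at when an event began, and not at whether its severity changed, does not fully serve that endpoint.

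The result also sits oddly with the cautious intent of 6.3. A trivial event with a missing date is counted, while a dated pre-surgery event that becomes serious after dosing is not. For laboratory and CSF data the SAP does look for deterioration: 7.9.2 and 7.9.3 list values that became clinically significant after baseline and were not so at baseline. AEs have no counterpart.

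**Working it through.** The plan states no figure on this point, so the check is of the text, followed by the direction and scale of any effect.

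**1. How an AE is classified.** Let S be the date of the first IDDD surgery in HGT-SAN-055.

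| Case | Treatment-emergent under 7.9.1 and 6.3? |
|---|---|
| Onset on or after S, including between S and first dose | Yes |
| Onset missing or partial, cannot be placed before S | Yes |
| Onset definitely before S, no later worsening | No, as intended |
| Onset definitely before S, worsens after S, worsening entered as a new AE | Yes, through the new onset date |
| Onset definitely before S, worsens after S, kept as one record | No |

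Only the last row is at issue.

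**2. Is there a worsening clause elsewhere?** None appears in the SAP or in its addendum. SAP 4.1 says that for AEs ongoing at entry to HGT-SAN-067 the extension record is used and the HGT-SAN-055 record dropped. It does not say which onset date the retained record carries, or how a change in severity is entered, so it does not settle the last row. The addendum's AE summaries are not limited to treatment-emergent events, but they cover only device-related AEs in the later safety follow-up period.

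**3. Does another AE output catch the event?** By title, 9 of 9 AE tables and 4 of 4 AE listings are restricted to treatment-emergent events. The text of 7.9.1 promises a listing of deaths without that qualifier, but the title of listing 12.2.7.3 adds it.

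**4. Direction.** Let A be the set of AEs counted now, and B the set counted once pre-surgery AEs that worsen on or after S are added. A is contained in B, so for any table cell the number of subjects under A is at most the number under B. The denominator is the dose group and does not change. Any difference is therefore an undercount.

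**5. Scale.** The number of AEs with onset before S is not given, so the size of the undercount cannot be derived. As a scale only: HGT-SAN-055 aimed for 4 completers per dose group (SAP 4.1), and the extension has at most 12 subjects (SAP 4.6). One subject is then 1/4 = 25 percentage points of a dose group of 4, or 1/12 = 8.3 points of 12. A cell moves only if that subject has no other event in it, because 7.9.1 counts recurrent AEs once per subject.

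**The case against.** The strongest reply is that the loss depends on a recording rule. Whether a rise in severity is entered as a new AE is normally set in the protocol or the case report form instructions, and SAP 2.1 refers the reader to the protocol for study conduct. If worsening is always a new record, nothing is lost. This stands, and it makes the point conditional. It does not remove it: the definition of the analysis set is the SAP's own, and as written it neither includes worsening nor says that the recording rule makes a clause unnecessary.

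It can also be said that the defining sentence does not mention onset, and that onset date appears only in the paragraph on uncertain cases. That is correct. Still, onset date is the only classifying variable the SAP names, and 6.3 asks whether the event occurred before surgery. The onset reading is the natural one, though it is not express.

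A third reply is that section 7 promises listings for every dataset, and that laboratory and CSF deterioration shows in the shift tables and the listings of clinically significant values. The general promise is narrowed by the AE listing titles in Appendix IV. The laboratory outputs help for laboratory and CSF findings but not for clinical events.

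A reader might infer three stronger things that the documents do not support:

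- That pre-surgery AEs are known to be in the data. A rule for incomplete dates shows only that the SAP allows for the case.
- That worsening of pre-existing disease symptoms in general is lost. Such symptoms may be held as medical history, which has its own listing (SAP 7.4), and the SAP does not say they were recorded as AEs before surgery.
- That 25 percentage points is the size of the bias. That figure applies to any single subject in a group of four and measures nothing about this rule.

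**Conclusion.** The point holds as a minor, conditional gap. SAP 7.9.1, read with 6.3, classes AEs by timing against the first IDDD surgery and has no clause for an AE with earlier onset that later worsens or becomes serious. Kept as one record, such an event is absent from all nine AE tables and all four AE listings of the treatment period, and the effect on the primary AE endpoint can only be downward.

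This rests on two assumptions: that onset date decides the classification, and that worsening is not always entered as a new AE. The second cannot be checked from the SAP. The exposure is narrow, because the window opens at the first surgery and events between surgery and first dose are already counted. The number of affected events is unknown and may be zero, so the documents do not support a claim that the safety tables are materially wrong.

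**What to change.** In SAP 7.9.1, define a treatment-emergent AE as one with onset on or after the first IDDD surgery in HGT-SAN-055, or with earlier onset that increases in severity or becomes serious on or after that date. State that an event of the second kind is counted at its worsened grade. Keep the partial-date rule of 6.3 and 7.9.1 as it is.

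If the protocol or the case report form instructions already require each worsening to be entered as a new AE with its own onset date, a sentence in 7.9.1 saying so would close the gap instead.

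The cost is one sentence and a small change to the treatment-emergent flag, which would need the date of worsening or of becoming serious. Table and listing titles stay the same. The only downside is that slightly more events may be reported.

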All subjects were to have an EOS visit 30 (\pm 7) days following their last administration of HGT-1410 (ie, Month 102); however, this extension study was discontinued early as efficacy criteria were not met in the Phase IIb safety and efficacy study, HGT-SAN-093, and the study did not yield clinical proof-of-concept and all studies in the Sanfilippo Syndrome Type A program have been discontinued. The EOS procedures included standard clinical laboratory tests (serum chemistry, hematology, and urinalysis) in CSF and blood, protocol specific laboratory testing (eg, anti-rhHNS antibody testing), neurodevelopmental testing, ABR, child health questionnaires, MRI and an X-ray examination of the device.

All subjects were to be contacted by telephone or have a visit for a Final Safety Follow up, to be conducted at 30 (\pm 7) days after the EOS visit to collect updated information on AEs and concomitant medications, therapies, and procedures.

It is anticipated that the IDDD would be used to obtain CSF samples and to deliver administrations of HGT-1410. However, if a subject's IDDD appeared nonfunctional or if its use was precluded on a scheduled day of dosing, site personnel were to refer to the operations manual (for the PORT-A-CATH IDDD) or the IDDD Manual (for the SOPH-A-PORT Mini S

IDDD), which describes the investigation and management of IDDD-related issues. This included possible partial revision or complete replacement of the IDDD. As noted above, a maximum of 2 partial revisions and/or complete replacements could occur in any 6-month period. If revision or replacement of the IDDD could not be scheduled in time to avoid a delay of the next scheduled dose of HGT-1410, or if the subject experienced more than 2 IDDD malfunctions in a 6-month period (including participation in study HGT-SAN-055), HGT-1410 was to be administered via lumbar puncture (LP). Study drug may have been administered via LP for a maximum of 5 successive monthly doses, after which, IDDD re-implantation or revision must have occurred.

If there was no significant safety risk in the opinion of the Investigator, a non-functional IDDD may have been left in situ for up to 3 months.

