In light of the higher than expected complications experienced with the PORT-A-CATH IDDD, the SOPH-A-PORT Mini S device was introduced for those subjects requiring replacement or revision. This device has design features anticipated to reduce complications encountered with the PORT-A-CATH IDDD device. Specific device assessments were included in the protocol to collect information with respect to information specific to SOPH-A-PORT Mini S device safety and function.

Subjects who discontinued or were withdrawn before receiving 3 monthly IT injections were not have to have undergone the EOS evaluations but were to have their IDDD removed.

In the protocol, it was planned that subjects were to have the IDDD removed when they discontinued from the study, unless the subject was continuing to receive treatment through another mechanism (eg, extension study, expanded access, commercially available). However, during study close out after the study was discontinued early, it was determined that some investigators would prefer to not remove the IDDD for some subjects unless a safety concern arises.

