7.5 Treatment Compliance and Extent of Exposure

Drug administration information will be presented by summarizing the duration of study drug exposure (weeks), the actual average dose (mg) and the number of infusions received.

The duration of IT administration is calculated by subtracting the IT administration start time from the IT administration end time.

By-subject listings of lot numbers of rhHNS received will be presented. A listing for drug administration including duration of administration will be presented by subject.

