2. RATIONALE FOR THE ADDENDUM

Study HGT-SAN-067 is an open-label, long term, multicenter, extension of Study HGT-SAN-055. The study was designed to evaluate the long-term safety, clinical activity, and biomarker outcomes of intrathecal (IT) administration of 3 dose levels (10 , 45 , and 90 mg once per month [Q4W]) of recombinant human heparan N-sulfatase (rhHNS, HGT-1410) via an intrathecal drug delivery device (IDDD) in subjects with Sanfilippo Syndrome Type A (MPS IIIA) who successfully complete the Phase I/II study HGT-SAN-055 (including end of study [EOS] assessments) and elect to continue to receive HGT-1410 treatment. The statistical analysis plan (SAP) for interim analysis dated on 24 March 2017 provided a technical and detailed elaboration of the planned interim analysis based on the data with cut-off date of 30th January 2017 (treatment period) for protocol HGT-SAN-067 amendment 8.

During the treatment period, if a subject discontinued, or withdrew from the study, or the study was stopped by the sponsor, the IDDD was to be removed. If the investigator determined that the IDDD should not be removed (full or partial device) from the subject based upon a safety assessment, then the subject continued in the study under the safety follow-up period upon completion of their last treatment period visit. The safety follow-up period of study HGT-SAN-067 will monitor the safety of the device up to an additional 3 years or until the device is removed in the last subject.

As of 28 February 2019, Study HGT-SAN-067 is considered complete as the sponsor has determined that the safety follow-up period may be ended as no safety concerns have been raised and subjects will continue to be monitored by their physicians. This SAP addendum for the safety follow-up period provides the planned analysis on the safety of the device for the subjects who did not have the IDDD removed (full or partial) at the end of the treatment period, based on protocol HGT-SAN-067 Amendment 8, dated 01 February 2017.

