6.5 Safety Analysis

6.5.1 Adverse Events

Device-related AEs were recorded throughout the safety follow-up period. AEs will be coded using the Medical Dictionary for Regulatory Activities (MedDRA) version 13.1 or higher.

AEs will be summarized descriptively. The summary will include the number and percentage of subjects with any AE, device surgical procedure related AE, device-related AE, any device-related serious AE (SAE), and any AE that lead to discontinuation.

AEs will be summarized by system organ class (SOC) and preferred term. The number and percentage of subjects experiencing an AE will be tabulated. Furthermore, AEs deemed as possibly/probably or definitely related to device surgical procedure, or IDDD will be summarized separately. SAEs and AEs which lead to study discontinuation will be similarly summarized.

By-subject listings will be provided for device-related AEs, device-related AEs resulting in death, SAEs, and AEs leading to discontinuation.

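### Adverse events are tabulated only as subjects affected; event counts and events per subject-year should be added, because follow-up is long and can differ between subjects

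*SAP*

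**What the plan says.** SAP Section 7.9.1 sets the overall AE summary on a subject basis: "The summary will include the number and percentage of subjects with any AE, any drug-related AE, any surgery-related AE, any IDDD-related AE", followed by further categories on the same basis. For the tables by organ class and preferred term it adds: "The number and percentage of subjects experiencing an AE will be tabulated; recurrent Aes observed within a subject will be counted once". The titles of Tables 10.3.1.1 to 10.3.1.9 in Appendix II mention no event count, person-time rate or time-to-onset display.

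The treatment-emergent window runs "from the time of the surgery for first IDDD implantation in HGT-SAN-055 to the last day of reporting period (or cut-off date". Section 4.1 places the planned end 30 days after the "last administration of HGT-1410 (ie, Month 102); however, this extension study was discontinued early". The addendum (Section 2) refers to a "planned interim analysis based on the data with cut-off date of 30th January 2017 (treatment period").

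Exposure is summarised separately in Section 7.5 as "duration of study drug exposure (weeks), the actual average dose (mg) and the number of infusions received". It is not linked to AEs.

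Section 4.1 explains why a second device was introduced: "In light of the higher than expected complications experienced with the PORT-A-CATH IDDD". It also has rules for more than two device malfunctions within 6 months. Device exposure and failures are listed only (the second section numbered 7.9.2), and Section 8 names the IDDD analysis among the data that will not be analysed.

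For the safety follow-up period, addendum Section 6.5.1 says: "The number and percentage of subjects experiencing an AE will be tabulated". It does not repeat the rule that recurrences count once. Addendum Section 6.4 defines a duration that ends at device removal or at the end of follow-up, whichever comes first.

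**The concern.** The primary objective is long-term safety and tolerability, and AEs are among the primary endpoints. A percentage of subjects ever affected is a cumulative quantity that grows with observation time even when the underlying rate is constant. Two groups followed for different times can therefore differ in the table without differing in risk. For frequent events, two groups with different rates can look alike.

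Recurrence matters in this trial because the implanted device can fail repeatedly, and the SAP foresees this. A subject with one device-related event and a subject with several under the same preferred term contribute the same entry. Since device failures are otherwise only listed, the AE tables are the only tabulated evidence on device complications, and they do not show how often these occur.

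**Working it through.** **Inputs from the SAP.** At most 12 subjects (Section 4.6) and about 4 per dose group (Section 4.1). Planned treatment to Month 102, which is 102/12 = 8.5 years, stopped early. The SAP gives no AE rates, entry dates, withdrawal counts or follow-up times, and has no figure of its own on this point to reproduce.

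**Assumptions.** Constant event rate r per subject-year, with r from 0.02 to 1. Follow-up T of 24, 54, 78 or 102 months.

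**Percentage affected.** P(at least one event) = 1 − exp(−r × T/12).

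| r per year | 24 mo | 54 mo | 78 mo | 102 mo |
|---|---|---|---|---|
| 0.02 | 3.9% | 8.6% | 12.2% | 15.6% |
| 0.1 | 18.1% | 36.2% | 47.8% | 57.3% |
| 0.25 | 39.3% | 67.5% | 80.3% | 88.1% |
| 0.5 | 63.2% | 89.5% | 96.1% | 98.6% |
| 1 | 86.5% | 98.9% | 99.8% | 100.0% |

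**Same rate, different follow-up.** At r = 0.25: 1 − exp(−0.25 × 2) = 39.3% at 24 months, and 1 − exp(−0.25 × 6.5) = 80.3% at 78 months.

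**Doubled rate, same follow-up (78 months).**
- 0.5 against 1 per year: 96.1% against 99.8%. The chance that both groups of four read 4/4 is (0.961 × 0.998)^4, about 0.85.
- 0.1 against 0.2 per year: 47.8% against 72.7%, so the contrast survives for less frequent events.

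**What counts and rates would show.** Four subjects followed for 6.5 years give 4 × 6.5 = 26 subject-years. At 0.5 and 1 per year the expected counts are 13 and 26 events, so the doubling is visible. The weakness is also visible: 13 events in one child and none in the other three give 13/26 = 0.5 per year, the same as 3.25 events in each child.

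**Limit set by group size.** With 4 against 4, a two-sided Fisher exact test gives p = 0.029 for 0/4 against 4/4, and p = 0.14 for 0/4 against 3/4. The SAP plans no such test; the figures only show how little a comparison of four with four can carry.

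**The case against.** The strongest reply is that subject incidence with full listings is a workable descriptive choice for at most 12 subjects. Several parts of it stand.

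- A reader might infer that recurrences are lost. They are not: Section 7.9.1 plans by-subject listings of all treatment-emergent AEs, and Listing 12.2.5.2 covers device exposure and failures. Recurrences can be counted there by hand. They are not summarised, and the AE listings supply no denominator.
- A reader might infer that all percentages approach 100%. Under the assumed rates this holds only from about 0.5 per year upwards. Events with different preferred terms also appear in separate rows; they collapse only within a term, within an organ class or in the overall summary.
- A reader might infer that the dose groups certainly differ in follow-up. The documents do not show that. Subjects' windows can differ through implantation date, withdrawal and early termination, but later entry of the higher dose groups is only an inference from the dose-escalation design.
- A reader might blame the metric for the lack of dose comparison. With about 4 subjects per group, comparison is weak on any scale. The 10 mg column also contains time at 45 mg, because Section 4.1 keeps subjects under their original arm.
- The AE endpoint is worded as type and severity, and both are tabulated. The study is descriptive and tests nothing.
- Splitting events by device type needs attribution rules, and Section 6.3 does not impute partial AE dates.

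The objection does not explain why a multi-year safety summary should omit event counts and observation time when the data for both are collected.

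**Conclusion.** The point holds in a limited form. The AE tables and the addendum's AE summary report subjects affected, without event counts or person-time. For the any-AE, organ-class and frequent or recurrent device- and procedure-related rows, they do not show frequency and they mix risk with length of follow-up. The size depends on assumed constant rates and follow-up times: a doubling of risk can almost vanish (96% against 99.8%), and an equal risk can look twofold different (39% against 80%). Rare terms are little affected by saturation.

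This is not a contradiction in the plan and invalidates no analysis. The documents do not support the stronger conclusion that the long-term safety question cannot be answered or that dose differences cannot be seen. It is a cheap improvement to the tables of a primary safety endpoint.

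**What to change.** Keep n (%) in Tables 10.3.1.1 to 10.3.1.9 and add the following by dose group:

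- the number of events;
- subject-years from first IDDD implantation to the end of reporting, so that the denominator matches the AE window (the drug exposure in Section 7.5 is a different quantity);
- events per subject-year.

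In the 10 mg group, split events and time by dose at onset (10 or 45 mg). In the addendum, show device-related events per unit of device time, using the duration defined in its Section 6.4.

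As a secondary step, where the onset date and the device in place are known, count IDDD- and surgery-related events by device type (PORT-A-CATH or SOPH-A-PORT Mini S), with an unassignable category for the rest. This step needs written attribution rules, for example for partial revisions, non-functional devices left in place and doses given by lumbar puncture.

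The main step costs a few columns from data already collected. The drawback is that one child can dominate a rate when a group has about 4 subjects. The subject count should therefore stay beside each rate, and the rates should be labelled descriptive.
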